## **VI. Randomization and Blinding**

We will use standard randomization to allocate patients in a 1:1 allocation to the TCD or the standard hysteroscopy drape. The randomization lists will be generated by a study statistician within [name] team using SAS Enterprise Guide version 6.1. The assignments will be opaque envelopes which ensure allocation

concealment. Once a patient consents and is deemed eligible for the study, the study coordinator will provide the next envelope to the operation nurse who will open the envelope in privacy to learn the allocation. All study staff collecting and recording data for the trial will be masked to the drape that was used during the procedure.

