## VIII. Statistical Methods and Sample Size Justification

The primary outcome for the study is the hysteroscopy fluid deficit (HFD) as determined by the fluid management system by subtracting the outflow volume (OV) from the inflow volume (IV) ( $HFD = IV - OV$ ). Our null hypothesis is  $H_0: \mu_{Standard} = \mu_{TCD}$  where  $\mu$ =mean fluid deficit. Our alternative hypothesis is  $H_a: \mu_{Standard} > \mu_{TCD}$  due to the underestimation of the outflow volume created by the loss of outflow fluid to floors and blankets. If we assume the true absorption rates by the patients are the same between the groups due to randomization, by estimating and testing the difference HFD between the two groups we are estimating and testing a more accurate measure of the uncollected fluid volume (UFV) as shown below:

$$\begin{aligned} \mu_{Standard} - \mu_{TCD} &= (\mu_{Standard, \text{true absorption}} + \mu_{Standard, \text{UFV}}) - \mu_{TCD, \text{true absorption}} \\ &= (\mu_{\text{true absorption}} + \mu_{Standard, \text{UFV}}) - \mu_{\text{true absorption}} \\ &= \mu_{Standard, \text{UFV}} \end{aligned}$$

The primary analysis for the study will use a general linear model on the HFD with a fixed effect for study group (TCD versus Standard drape) controlling for surgeon and indication for hysteroscopy, the stratification factors for the randomization.

Secondary outcomes include estimated uncollected fluid volume from floor and blankets, occurrence of the fluid deficit alarm sounding, stopping of the operation due to concerns of overabsorption by the patient, and adverse events. Estimated uncollected fluid volume will be analyzed similar to the primary outcome. All other outcomes are categorical and will be compared using Chi-square analyses.

We will sample 10 procedures (or until data saturation) from each arm (TCD vs standard) to conduct qualitative assessments on Usability using the Human Factors

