Assessment Tool for the surgeons and operating team members. Once data saturation is reached using the Human Factors Assessment Tool, enrolled surgeons will be provided a step-by-step video link orientation to the Total Capture Drape. For the SUS, we will collect data on attending physicians only on their first and fifth procedures (the study team may change it to 1st and 3rd if deemed appropriate). We will estimate means or medians with standard deviations (or interquartile ranges) for the items and total scores for the SUS. Both within (1st vs. 5th) and between arms (TCD vs. standard) comparison on total scores of SUS will be conducted. We will compare the two groups using linear mixed models or generalized linear mixed models (depending on the distribution) with a random effect for the procedure to control for correlation of the measures among team members participating in the same procedure.

At this early stage of investigation, we have no prior data on HFD in patients to estimate the variability need for the sample size estimation. We have preliminary data from the simulated experiment showing a 100% recovering of loss deficit by the TCD. If we conservatively assume the loss deficit will decrease from 40% to 20% of the inflow volume, this would result in a clinically meaningful improvement with an approximate effect size of 0.92 based on the variability of loss deficit in the simulation. Given this, we are using effect size (relative to standard deviation) as the primary justification for the number of patients needed for the study. With a sample size of n=34 per arm, we would have 81% power to detect an effect size of 0.7 (0.7\*standard deviation of the HFD) with a two sided, two sample t-test ( $\alpha=0.05$ ). To account for potential missing data of 10%, we propose randomizing 76 women (n=38 per arm). With n=34 women in each group, we would also have 80% power to detect an absolute 33% reduction in the proportion of procedures with the alarm sounding due to fluid deficit threshold being reached assuming the proportion in the standard drape arm is 50%. This power was calculated using a Fisher's Exact test for testing proportions between two independent samples. The same power would apply for detecting differences in the proportion of procedures terminated.

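### Alarm and stopping outcomes are compared without the stratification factors used for the fluid outcomes; stratifying by indication is a modest, low-cost efficiency gain

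*Combined protocol and SAP*

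**What the plan says.** Section VIII fits a general linear model to the fluid deficit, "controlling for surgeon and indication for hysteroscopy, the stratification factors for the randomization". It treats the continuous secondary outcome in the same way: "Estimated uncollected fluid volume will be analyzed similar to the primary outcome". For the alarm, stopping for suspected overabsorption, and adverse events, the rule is different: "All other outcomes are categorical and will be compared using Chi-square analyses". No adjustment or stratification is mentioned there, and no reason is given for the difference.

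The alarm has its own power claim in the same section: "80% power to detect an absolute 33% reduction in the proportion of procedures with the alarm sounding". It assumes 50% in the standard arm, 34 women per arm and an unadjusted Fisher's exact test. The plan says the same power applies to terminated procedures.

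Section VI describes the allocation differently from Section VIII: "We will use standard randomization to allocate patients in a 1:1 allocation to the TCD or the standard hysteroscopy drape". It adds that "the study coordinator will provide the next envelope to the operation nurse", and mentions no strata, blocks or separate envelope sets. The documents do not give the number of surgeons, the indication categories or a block size.

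**The concern.** When allocation is balanced within strata that predict the outcome, the difference between arms varies less from trial to trial than an unadjusted chi-square assumes. The test then rejects less often than its nominal 5% under the null and gives up some power under the alternative. An analysis by stratum removes this.

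There is some reason to expect indication to matter. Section II ties absorption to how invasive the surgery is, Section III describes the alarm as a threshold on the deficit, and the sponsor names indication as a stratification factor. The alarm and premature stopping are also the outcomes nearest to the patient's experience (Section II). With 34 evaluable women per arm, a few points of power are worth having if they cost almost nothing.

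**Working it through.** **1. The plan's own figures.** The primary power statement, "With a sample size of n=34 per arm, we would have 81% power to detect an effect size of 0.7" "with a two sided, two sample t-test", reproduces at 81.2%. For the alarm, alpha and sidedness are not restated, so two-sided 0.05 is assumed. Exact enumeration of two binomials, n = 34 per arm:

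- Fisher's exact, 50% vs 17%: 77.9%. If 33% is a rounded one-third (50% vs 16.7%): 78.9%. The stated 80% is reproduced within that rounding.
- Pearson chi-square, the planned test, 50% vs 17%: 85.3%. Type I error at a common rate of 50%: 4.5%.

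With one common alarm rate, the planned test therefore exceeds the stated 80%.

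**2. Adding an indication effect.** Assumptions, none of them from the documents: three equally likely indications, permuted blocks of 4 within indication, N = 68, and a common odds ratio chosen so that the TCD arm averages 17%. The tests are Pearson chi-square and CMH by indication, where CMH = [Σ(aₖ − Eₖ)]² / ΣVₖ. Here aₖ is the number of TCD alarms in stratum k, and Eₖ and Vₖ are its hypergeometric mean and variance.

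| Standard-arm alarm rates by indication | Chi-square power | CMH power | Gain (points) |
|---|---|---|---|
| 50/50/50% | 84% | 83% | −1 |
| 35/50/65% | 85% | 85% | 0 |
| 20/50/80% | 87% | 91% | +4 |
| 10/50/90% | 89% | 96% | +7 |

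Type I error with stratified allocation is about 2% for chi-square at 20/50/80% and about 1% at 10/50/90%. CMH stays at about 4 to 5%.

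**3. If allocation is not stratified**, as Section VI reads. Chi-square type I error is 4.3 to 4.8%, so the added conservatism disappears. CMH still gains when indication is prognostic: 70% vs 77% at 20/50/80% with a TCD mean of 22%. It costs about 2 to 2.5 points when indication is not prognostic.

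**4. Why surgeon should stay out of the strata.** With 40 sparse strata that carry no prognostic information, power is 85.1% for chi-square and 66.6% for CMH, a loss of 18.5 points. With 4 strata the difference is −0.9, +2.9 or +6.6 points for no, moderate or strong prognosis.

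**5. Where an exact fallback should trigger.** Each of three strata holds 68/3 ≈ 22.7 women, about 11.3 per arm. The average planned alarm rate is (50% + 17%)/2 = 33.5%, so the expected alarms per stratum and arm are 11.3 × 0.335 ≈ 3.8. A rule of expected count below 5 applied per stratum would trigger in about 99 to 100% of trials. The exact stratified test would then replace CMH and remove most of the gain. At 20/50/80% with a TCD mean of 19%, power is 81% (chi-square), 86% (CMH) and 82% (exact). With no prognosis it is 85%, 85% and 81%.

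On the pooled table, the expected alarms per arm are 34 × 0.335 ≈ 11.4, so the rule does not trigger at the planned alarm rates. It would for a rare stopping outcome: at 20% vs 2%, expected events per arm are 34 × (0.20 + 0.02)/2 ≈ 3.7.

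**The case against.** The strongest case against is that the unadjusted test is valid, matches the unadjusted basis of the power calculation, and concerns secondary outcomes only. Nothing in the documents quantifies how far indication predicts the alarm. Section II speaks of invasiveness and distention pressure, not indication. Sections II and IV attribute false deficits to leakage and adhesive failure, which need not follow indication. At 35/50/65% the two tests are equivalent. All of this stands, and it limits the point to a conditional efficiency gain.

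A reader might infer that the planned test falls short of the stated 80%. The calculations do not support that: at 50% to 17%, chi-square power is 84 to 89% in every scenario in the table. A contrast of 59% vs 77% can be produced at 10/50/90%, but there the TCD mean is about 25%, a reduction of 25 points and not the planned 33.

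A reader might also infer that the chi-square is conservative in this trial as a fact. That requires allocation balanced within strata, which Section VIII asserts and Section VI does not describe.

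The objection does not show that the unadjusted test is preferable. The trial already treats indication as a design factor and uses it for the fluid outcomes, and the likely loss from using it here is small.

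**Conclusion.** The inconsistency is real and its consequence is modest. If allocation is stratified as Section VIII says and indication strongly predicts the alarm, the chi-square is conservative (about 2% at 20/50/80%) and gives up about 4 to 7 points of power at the planned effect. With a weakly prognostic indication it gives up nothing. Type I error is not inflated and the plan's 80% is not undercut, so no conclusion of the trial would be invalid.

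These sizes rest on assumed alarm rates, three equal indications, blocks of 4 and a common odds ratio. They apply to the alarm. For stopping, the stated power holds only if about half of standard-drape procedures are also stopped. If stopping is rare, the exact fallback would apply and no gain should be claimed.

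**What to change.** In Section VIII, replace the chi-square for the alarm and stopping outcomes with a CMH test stratified by indication. Pool indication in advance to a few named levels and leave surgeon out of the strata. Report the Mantel-Haenszel risk difference with its 95% CI. Use the exact stratified test only when the outcome is rare overall: an expected count below 5 in the pooled arm-by-outcome table, or the Mantel-Fleiss criterion not met. State explicitly that per-stratum counts do not trigger it.

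Reconcile Section VI with Section VIII: say whether allocation is stratified and, if so, give the strata, the blocking and how envelopes are kept by stratum.

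No new data are needed, since indication is already required for the primary model. The downside is about 1 point of power if indication does not predict the outcome, and up to about 2.5 points if allocation is also unstratified. If surgeon is a true stratification factor and is itself prognostic, some conservatism will remain. That is the price of avoiding sparse strata.

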**I. Specific Aims:**

- a) To perform a comparative trial of the “Total Capture” hysteroscopy drape (TCD) versus the standard drape during patient surgeries to document improved, real-time determination of patient fluid absorption. Inaccurate detection of fluid absorption by a patient during hysteroscopy is a source of complications, morbidity and mortality from excessive patient fluid absorption. Pilot testing of a prototype design of the “Total Capture” drape versus the conventional hysteroscopy drape indicated remarkable improvement in fluid capture and accurate fluid deficit determination in a plastic pelvic model experiment. The interest from corporate producers of hysteroscopy fluid management systems and drape manufacturers is contingent upon demonstrating “proof of concept” with actual patient surgeries.
  
- b) To evaluate the clinical usefulness of the TCD compared to the Standard drape for hysteroscopy with the standardized metrics of: 1) the Human Factors Surgical Drape Assessment and 2) The System Usability Scale. These metrics will allow us to quantitate clinical usefulness and usability of both the operating surgeons and operating room staff.

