#### **Measures for Drape Usability, Quality, and Convenience**

We plan to objectively and subjectively evaluate the usability and usefulness of the TCD compared to the standard drape. Staff will be asked to complete the System Usability Scale (SUS) [section XVII SUS; Brooke, 1986] to evaluate their perceived clinical usefulness of the TCD and the standard drape. The SUS is a validated 10-item survey for assessing perceived usability that uses a 5-point Likert scale ranging from strongly disagree to strongly agree. To further subjectively and objectively assess the TCD a human factors and design researcher will observe the surgeries. The human factors researcher will attend the first surgeries to ensure consistent rating with design researcher who will subsequently observe the remaining surgeries until data saturation is reached. The human factors expert will attend any surgeries the design researcher cannot attend. Staff will be asked to speak aloud using the system, which the researcher will record. Further, the researcher will complete an objective human factors assessment tool (section XVII). Finally, enrolled surgeons will be provided the opportunity to participate in one-on-one feedback sessions or focus group sessions to provide suggestions on how they perceive usability of the drape can be improved. These sessions will be facilitated by the Principal Investigator and the design researcher or human factors expert. These metrics will allow us to quantitate clinical usefulness and usability of both the operating surgeons and operating room staff. These results will not only provide this assessment of the TCD compared to the standard hysteroscopy drape (which is used across ORs within CHS) but will also provide important information to improve the drape if deficiencies are identified.

Adverse events and serious adverse events will be captured along with relatedness and severity. We will classify event terms using Common Terminology Classification of Adverse Events version 4.03 (National Cancer Institute).

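### The measures section has staff complete the SUS, but Section VIII collects it from attending physicians only and then applies a model that needs several raters per procedure

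*Combined protocol and SAP*

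**What the plan says.** Three places in the combined protocol and SAP bear on who completes the SUS.

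- **Section I, Aim b** names two instruments, "1) the Human Factors Surgical Drape Assessment and 2) The System Usability Scale", and says of them together: "These metrics will allow us to quantitate clinical usefulness and usability of both the operating surgeons and operating room staff".
- **Measures for Drape Usability, Quality, and Convenience** says "Staff will be asked to complete the System Usability Scale (SUS", with the purpose "to evaluate their perceived clinical usefulness of the TCD and the standard drape". The same section has staff speak their thoughts aloud while a researcher records them, and has the researcher fill in the human factors tool. It repeats Aim b's sentence about surgeons and operating room staff.
- **Section VIII** says "For the SUS, we will collect data on attending physicians only", at each attending's first and fifth procedures, with the option of moving the second time point to the third procedure. It plans comparisons of SUS totals within arms (first against fifth) and between arms. The model that follows has a random effect for procedure "to control for correlation of the measures among team members participating in the same procedure".

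Section VIII also applies the human factors tool to surgeons and operating team members. It calls that work qualitative and samples 10 procedures from each arm, or continues until saturation.

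**The concern.** The measures section and Section VIII cannot both be followed. A coordinator working from the first hands SUS forms to staff. One working from the second hands them to attendings alone, and no section sets a time for anyone else to complete the form.

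Two things are at stake. The first is whose view the SUS represents. Clinical Study Design puts the circulating nurse in charge of the fluid management system and has that nurse determine the uncollected volume, so at least one non-physician is a direct user. Section XIII also expects data on the satisfaction of both surgeons and operating room staff. The second is the analysis. The model is written for several people rating the same procedure, which the attendings-only rule does not produce.

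**Working it through.** The plan gives no sample size or power figure for the SUS, so there is no stated number to reproduce. The check compares the texts and then examines the model's structure.

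**1. Who completes the SUS**

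| Section | SUS respondents |
|---|---|
| Aim b | Not assigned; two metrics jointly cover surgeons and staff |
| Usability measures | Staff, for both drapes |
| VIII, collection rule | Attending physicians, first and fifth (or third) procedures |
| VIII, model | Several team members in one procedure |

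Under the collection rule, the number of staff SUS scores is 0 in each arm.

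**2. What remains for staff**

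The human factors sample is 10 procedures per arm, so 2 × 10 = 20 procedures. The plan randomizes 76 women, and 20 / 76 = 26%. The actual count may differ because saturation can end the sampling. The tool is completed by the observing researcher, and the spoken comments are recorded by the researcher. Neither is a score that staff give themselves.

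**3. The procedure random effect with one rater**

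Write the score of rater k in procedure j as

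y_jk = μ + β·arm_j + p_j + e_jk, with variances σ²_p and σ²_e.

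The covariance matrix is V = σ²_p ZZ′ + σ²_e I, where Z links ratings to procedures.

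- With several raters per procedure, two ratings from the same procedure have covariance σ²_p, so σ²_p can be estimated.
- With one rating per procedure, Z = I and ZZ′ = I (confirmed numerically for six procedures). Then V = (σ²_p + σ²_e) I. Only the sum can be estimated, and the linear mixed model reduces to ordinary regression with independent errors.

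**4. The correlation that does arise**

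Each attending is to give a rating at a first and a fifth procedure. These are different procedures, so the planned term gives them covariance 0. If surgeons differ in their general level of scoring, with variance σ²_s, the true covariance is σ²_s. Let σ²_w be the remaining variance and ρ = σ²_s / (σ²_s + σ²_w). For the difference between a surgeon's two ratings:

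- variance under the planned model: 2(σ²_s + σ²_w)
- true variance: 2σ²_w
- ratio: (σ²_s + σ²_w) / σ²_w = 1 / (1 − ρ)

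For any ρ above 0, the first-against-fifth contrast is given too large a variance. For the comparison between drapes the direction depends on the data. Treating a surgeon's repeated ratings of one drape as independent understates the variance. Ignoring that one surgeon rated both drapes overstates it. The documents give no value of ρ, so no figure is attached.

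**The case against.** **Aim b does not promise SUS scores from staff.** This stands. A reader might infer such a promise, but Aim b assigns its two metrics jointly, and the human factors tool could satisfy it for staff. The explicit statement that staff complete the SUS is in the measures section.

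**Staff usability is not unmeasured.** This also stands. A reader might conclude that half of Aim b has no data, but the human factors tool covers operating team members, the measures section describes it as objective, and staff comments are recorded. What is missing is a SUS score from staff.

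**Attendings only is a defensible choice.** Section IV has the surgeon position the drape using the hand pouches, so the surgeon is a principal user. The choice is acceptable if the other text is brought into line. Nor do the documents support a broad claim about the whole team's role with the fluid system: they name the circulating nurse and mention no scrub person.

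**The word restricting the rule might attach to the procedures and not to the physicians.** Even so, attendings remain the only respondents with a SUS schedule.

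**The random effect might be meant for the human factors data.** The sentence does not name the SUS, but it directly follows the planned SUS comparisons. If it was meant for the other tool, the SUS comparisons have no stated model.

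**The consequences are limited.** Agreed. The SUS is not among the listed secondary outcomes, carries no power claim, and has no bearing on the fluid deficit, the alarms or safety.

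**Conclusion.** The conflict is real and lies in current text. Following Section VIII gives no staff SUS score in either arm, and staff usability then depends on observer-completed and recorded material from about 20 of 76 procedures, or until saturation. The random effect cannot be identified in a linear mixed model with one rating per procedure, while repeated ratings by the same surgeon go unmodelled.

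This rests on three readings: that staff in the measures section includes people other than surgeons, as the separate naming of the two groups there suggests; that normally one attending rates each procedure; and that the model sentence applies to the SUS. The point concerns a secondary aim and should be settled before SUS data are collected. The fluid deficit analysis does not depend on it.

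**What to change.** Choose one of two options and make the three sections agree.

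**(a) Collect staff ratings.** In Section VIII, have operating room staff, such as the circulating nurse, also complete the SUS at the scheduled SUS procedures in both arms. Report surgeon and staff scores separately. Use staff scores only to compare drapes: an attending's first and fifth procedures need not be a staff member's first and fifth, so the within-arm contrast has no clear meaning for staff. Fit random effects for rater and for procedure, since the same staff member may rate more than once.

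**(b) Keep attendings only.** Restrict the SUS sentence in the measures section, and the SUS part of Aim b, to attending physicians. Replace the procedure random effect with a surgeon random effect.

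Option (a) costs one 10-item form for each added rater at procedures where the SUS is already collected, plus identification of raters in the data. Option (b) costs only text changes, but leaves a narrower stated aim.

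### The SUS is timed by each surgeon's procedure count without saying whether the count is per drape, so the planned 1st-vs-5th comparison is confounded or very imprecise

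*Combined protocol and SAP*

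**What the plan says.** On timing, Section VIII collects the SUS from "attending physicians only on their first and fifth procedures". It adds that "the study team may change it to" the first and third procedures, and gives no criterion or deadline for that decision. Total scores are then to be compared in two ways: within (1st vs. 5th) "and between arms (TCD vs. standard) comparison on total scores of SUS will be conducted". The analysis is a linear or generalised linear mixed model whose only named random effect is for procedure, meant for ratings by several team members at one operation. No surgeon effect and no drape-by-occasion term is named.

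The drape is assigned patient by patient. Section VI describes "standard randomization to allocate patients in a 1:1 allocation to the TCD or the standard hysteroscopy drape". Section VIII has the primary model "controlling for surgeon and indication for hysteroscopy, the stratification factors for the randomization". No block size is given.

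Three further facts bear on this point:
- The usability subsection of Section V has staff completing the SUS, whereas Section VIII restricts it to attendings.
- Section VIII provides surgeons with an orientation video for the TCD once the human factors observations reach saturation.
- The number of surgeons is not given. Nothing says that a surgeon keeps one drape, or how two ratings on different drapes are to be handled.

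**The concern.** A comparison of first with later ratings is the part of the SUS plan that could separate unfamiliarity with a new drape from lasting usability. That requires the two ratings to be tied to use of the same drape. Here the clock is the surgeon's operation count, while the drape changes at random between operations. Where the two ratings fall on different drapes, the change from first to fifth is also a change of drape. Even where the fifth procedure uses the TCD, it is usually not the surgeon's fifth TCD case.

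The two possible counting rules call for the form at different operations, so the coordinator cannot tell from the text when to hand it out. A rating missed at the time cannot be recovered afterwards.

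**Working it through.** **Inputs from the documents.** 76 randomised, 38 per arm; 1:1 by patient; ratings at procedures 1 and 5 (possibly 1 and 3). The 38 per arm follows from the plan's own figures: 34/0.9 = 37.8, rounded up. The stated 81% power concerns the fluid deficit and reproduces (81.2%). No power is stated for the SUS, so there is no SUS figure to reproduce.

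**1. Literal reading: chance that procedures 1 and 5 use different drapes.**
- Simple 1:1: 1 − (0.5² + 0.5²) = 0.50.
- One fixed 38/38 list: 38/75 = 0.507.
- Permuted blocks within surgeon, size 2 or 4: the two procedures lie in different blocks, so 0.50.
- Block sizes 6, 8, 10: 3/5 = 0.60, 4/7 = 0.571, 5/9 = 0.556.
- Blocks within surgeon by indication (assumed 2 or 3 indications, block sizes 2 to 6, simulated): 0.53 to 0.58.

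For procedures 1 and 3 the range is 0.50 to 0.67 (block of 4: 2/3).

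**2. Literal reading: number of pairs.** At most floor(76/5) = 15 surgeons reach a fifth procedure. Expected TCD–TCD pairs are 15 × (1 − p)/2, where p is the crossing probability: 3.75 at p = 0.50 and 3.0 at p = 0.60. With 8 surgeons (assumed) and p = 0.50, the expectation is 2 TCD pairs, 2 standard pairs and 4 crossing pairs, and the chance that at least one arm has fewer than 2 pairs is 64%.

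**3. Literal reading: TCD experience at procedure 5.** Under simple allocation, a surgeon using the TCD at procedure 5 has used it 1 + 4 × 0.5 = 3 times on average, counting that case.

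**4. Per-drape reading.** No pair crosses. At most floor(38/5) = 7 surgeons can supply a 1st/5th pair for a given drape, and a surgeon needs at least 10 cases to do so for both. With exactly 10 cases, the chance of five on each drape is 252/1024 = 25% under simple allocation, and 100%, 67% or 60% with surgeon blocks of 2, 4 or 6. For 1st/3rd use the ceiling is floor(38/3) = 12 surgeons. The chance of three on each drape is 89% with 10 cases under simple allocation. With 7 cases it is 55% under simple allocation and 100% with surgeon blocks of 2, 4 or 6.

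**5. Precision of the within-TCD change.** Take score SD = 1 and within-surgeon correlation ρ = 0.5 (assumed). The detectable change at 80% power is about 2.8 × √variance (normal approximation).

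| Approach | Variance | Detectable change |
|---|---|---|
| Literal, 15 surgeons, same-drape pairs only | 2(1−ρ)/3.75 = 0.267 | 1.45 SD |
| Literal, 15 surgeons, model with surgeon, drape, occasion and interaction | 2(1−ρ)(2+ρ)/15 = 0.167 | 1.14 SD |
| Per drape, 5th use, 7 surgeons | 2(1−ρ)/7 = 0.143 | 1.06 SD |
| Per drape, 3rd use, 12 surgeons | 2(1−ρ)/12 = 0.083 | 0.81 SD |

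For ρ from 0 to 0.7 the second row runs from 1.45 down to 0.92 SD. All four rows use ceilings on surgeon numbers. The approximation flatters tiny samples: exact paired t-tests need 3.3, 2.1 and 1.27 SD of the paired differences with 3, 4 and 7 pairs.

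**6. The planned model.** With one attending per procedure and attendings as the only raters, each procedure yields one score. In a linear mixed model a procedure effect then cannot be separated from residual error. The repeated structure that does exist, two ratings by one surgeon, is not modelled.

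**The case against.** A reader might infer that half the pairs will certainly cross drapes. The documents do not support that: a comparison within arms can mean first and fifth use of each drape, and then none cross. What is established is that the counting rule is not stated, and that both readings leave few pairs.

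A reader might also infer that the question cannot be answered. That does not follow either. A model with surgeon, drape and occasion uses crossing pairs, and its 1.14 SD is close to the 1.06 SD from counting fifth uses per drape. Most of the imprecision comes from the small number of surgeons. Two things remain against the plan: the model it names is not that one, and even the better model would measure change with procedure count, not with TCD use.

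Some further inferences also fail:
- That no surgeon could reach five on both drapes once eight or more share the cases equally. At eight, 76/8 = 9.5, so four surgeons would have 10 cases.
- That low reach probabilities under simple allocation settle the matter. Surgeon is named as a stratification factor, and blocking within surgeon raises them. The ceilings of 15 and 7 and the crossing rate of about half survive blocking.
- That the between-arm comparison at first use is biased because it is between surgeons. The drape at first use is randomised, so the comparison is unbiased and only less precise.

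On importance, the objection largely stands. Aim (b) in Section I concerns usability compared with the standard drape and does not mention learning. Observation, spoken comments and surgeon feedback sessions also inform it.

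**Conclusion.** The point holds in a limited form. The SUS timing is not tied to the drape. Read literally, 0.50 to 0.60 of the 1st/5th pairs cross drapes, and fewer than 4 TCD–TCD pairs are expected even with the maximum of 15 surgeons. Read per drape, at most 7 surgeons can supply a pair for a given drape. The named random effect does not repair either case. The within-arm comparison is therefore confounded or very imprecise as planned, but not unanswerable.

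The ceilings and the crossing range need only the plan's sample size and 1:1 allocation, plus a range of block sizes. The detectable changes also rest on assumed surgeon numbers and correlation, and the modelling remark on one attending per procedure. No stated figure is wrong. This is a cheap improvement of low priority, because the SUS is not among the secondary outcomes listed in Sections V and VIII and has no stated power.

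**What to change.** Before enrolment:

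1. State that procedures are counted per surgeon and per drape. Collect the SUS at each surgeon's first and third use of the TCD and first and third use of the standard drape. The protocol already allows first and third; fix that choice and delete the option to change it later.
2. At each rating, record the drape, the surgeon's cumulative TCD use, and whether the orientation video has been seen, since it can fall between two ratings.
3. Replace the procedure effect by a random effect for surgeon, with fixed effects for drape, occasion and their interaction. If staff ratings are also wanted, as Section V suggests, say so; a procedure effect would then have a role again.
4. Report the within-drape change as descriptive, with an interval. Section V describes the standard drape as already in use across the health system's operating rooms, so treat its first rating in the trial as a reference and not as a learning occasion.

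The cost is a few sentences of protocol text, a tally kept by the coordinator, and up to four short questionnaires per surgeon instead of two. The main drawback is that a third use shows less of the learning curve than a fifth. The number of surgeons, which limits precision most, is unchanged.
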